3.0540	Summary of Drug-Related Infections with Grade $\geq 3$ Reported as Adverse Events up to 60 Days after Last Treatment
3.0550	Summary of Serious Infections Reported as Adverse Events
3.0560	Summary of Serious Infections Reported as Adverse Events up to 60 Days after Last Treatment
3.0570	Summary of Serious Infections with Grade $\geq 3$ Reported as Adverse Events
3.0580	Summary of Serious Infections with Grade $\geq 3$ Reported as Adverse Events up to 60 Days after Last Treatment
3.0590	Summary of Serious Drug-Related Infections Reported as Adverse Events
3.0600	Summary of Serious Drug-Related Infections Reported as Adverse Events up to 60 days after Last Treatment
3.0610	Summary of Infections by Screening Binet Stage
3.0620	Summary of Infections by Screening Rai Stage
3.0630	Summary of Infections by Baseline Neutrophil Grade
3.0640	Overview of Infusion Related Adverse Events for the Ofatumumab Arm
3.0641	Overview of Infusion Related Adverse Events for the Ofatumumab Arm up to 60 Days after Last Treatment
3.0650	Summary of Infusion Related Adverse Events for the Ofatumumab Arm
3.0660	Summary of Infusion Related Adverse Events with Grade $\geq 3$ for the Ofatumumab Arm by Preferred Term
3.0670	Summary of Infusion Related Adverse Events By Maximum Toxicity Grade and by Preferred Term for the Ofatumumab Arm
3.0680	Summary of Time to First Infusion Reaction by Infusion for the Ofatumumab Arm
3.0690	Summary of Adverse Events Excluding Infusion Related Events by Preferred Term up to 60 Days after Last Treatment for the Ofatumumab Arm
3.0700	Summary of Adverse Events with Grade $\geq 3$ Excluding Infusion Related Events by Preferred Term up to 60 Days after Last Treatment

	for the Ofatumumab Arm
3.0710	Overview of Mucocutaneous Reactions Reported as Adverse Events
3.0720	Summary of Mucocutaneous Reactions Reported as Adverse Events
3.0730	Summary of Mucocutaneous Reactions Reported as Adverse Events up to 60 Days After Last Treatment
3.0731	Summary of Mucocutaneous Reactions Reported as Adverse Events by Preferred Term
3.0732	Summary of Mucocutaneous Reactions Reported as Adverse Events up to 60 Days After Last Treatment by Preferred Term
3.0740	Summary of Serious Mucocutaneous Reactions Reported as Adverse Events
3.0741	Summary of Serious Mucocutaneous Reactions Reported as Adverse Events by Preferred Term
3.0750	Summary of Adverse Events for Subjects with Adverse Events Considered Both Infusion Reaction Related and Mucocutaneous Reactions by Preferred Term
3.0760	Overview of Adverse Events Associated with Decreased Neutrophil Counts
3.0761	Overview of Adverse Events Associated with Decreased Neutrophil Counts Up to 60 Days after Last Treatment
3.0770	Overview of Grade $\geq 3$ Adverse Events Associated with Decreased Neutrophil Counts
3.0780	Summary of Adverse Events Associated with Decreased Neutrophil Count by Maximum Toxicity Grade and by Preferred Term
3.0790	Overview of Adverse Events Associated with Decreased Hemoglobin
3.0791	Overview of Adverse Events Associated with Decreased Hemoglobin up to 60 Days after Last Treatment
3.0800	Overview of Grade $\geq 3$ Adverse Events Associated with Decreased Hemoglobin
3.0810	Summary of Adverse Events Associated with Decreased Hemoglobin by Maximum Toxicity Grade and by Preferred Term
3.0820	Overview of Adverse Events Associated with Decreased Platelet Counts
3.0821	Overview of Adverse Events Associated with Decreased Platelet Counts up to 60 Days after Last Treatment
3.0830	Overview of Grade $\geq 3$ Adverse Events Associated with Decreased Platelet Counts
3.0840	Summary of Adverse Events Associated with Decreased Platelet Count by Maximum Toxicity Grade and by Preferred Term
3.0850	Overview of Adverse Events Associated with Other Cytopenias

3.0860	Overview of Grade $\geq 3$ Adverse Events Associated with Other Cytopenias
3.0870	Summary of Adverse Events Associated with Other Cytopenias up to 60 Days after Last Treatment
3.0880	Summary of Adverse Events Associated with Other Cytopenias with Grade $\geq 3$ up to 60 Days After Last Treatment
3.0890	Summary of Serious Adverse Events Associated with Other Cytopenias with Grade $\geq 3$ up to 60 Days After Last Treatment
3.0900	Summary of Autoimmune Hematologic Complication Adverse Events
3.0910	Summary of Autoimmune Hematologic Complication Adverse Events up to 60 Days after Last Treatment
3.0920	Summary of Serious Autoimmune Hematologic Complication Adverse Events up to 60 Days after Last Treatment
3.0921	Summary of Autoimmune Hematologic Complication Adverse Events by Preferred Term
3.0922	Summary of Autoimmune Hematologic Complication Adverse Events up to 60 Days after Last Treatment by Preferred Term
3.0923	Summary of Serious Autoimmune Hematologic Complication Adverse Events up to 60 Days after Last Treatment by Preferred Term
3.0924	Summary of AEs for Secondary Malignancies, Cardiac Events, Bowel Obstruction or Small Bowel Obstruction
3.0925	Summary of AEs for Secondary Malignancies, Cardiac Events, Bowel Obstruction and Small Bowel Obstruction Up to 60 Days After Last Treatment
3.0926	Summary of SAEs for Secondary Malignancies, Cardiac Events, Bowel Obstruction and Small Bowel Obstruction
3.0927	Summary of SAEs for Secondary Malignancies, Cardiac Events, Bowel Obstruction and Small Bowel Obstruction Up to 60 Days after Last Treatment
3.0928	Summary of AEs for Secondary Malignancies, Cardiac Events, Bowel Obstruction and Small Bowel Obstruction With Grade <math>\geq 3</math> Up to 60 Days After Last Treatment
3.0929	Summary of SAEs before or after start of next anticancer therapy
3.0930	Summary of Deaths
3.0940	Summary of Deaths up to 60 Days after Last Treatment
3.0950	Summary of Chemistry Laboratory Values
3.0960	Summary of Chemistry Laboratory Values Change from Baseline
3.0970	Summary of Chemistry Data Outside the Reference Range
3.0980	Summary of Chemistry Toxicities by Maximum Grade
3.0990	Summary of Chemistry Grade Shifts from Baseline Grade
3.1010	Summary of Hematology Laboratory Values

3.1020	Summary of Hematology Laboratory Values Change from Baseline
3.1030	Summary of Hematology Data Outside the Reference Range
3.1040	Summary of Hematology Toxicities by Maximum Grade
3.1050	Summary of Hematology Grade Shifts from Baseline Grade
3.1070	Summary of Human Anti-human Antibodies (HAHA) Over Time
3.1071	Summary of Human Anti-human Antibodies (HAHA)
3.1090	Summary of IgG, IgA, and IgM over Time
3.1091	Summary of IgG, IgA and IgM over time up to 60 days after last treatment
3.1100	Summary of Change from Baseline in IgG, IgA, and IgM Over Time
3.1110	Summary of Number of Subjects with Late onset Neutropenia and Prolonged Neutropenia
3.1112	Summary of Grade 3/4 Myelosuppression (Anemia, neutropenia, or thrombocytopenia)
3.1120	Summary of Vital Signs
3.1130	Summary of Vital Signs Change from Baseline
3.1140	Summary of Increases in Systolic Blood Pressure from Baseline
3.1150	Summary of Increases in Diastolic Blood Pressure from Baseline
3.1160	Summary of Increases in Heart Rate from Baseline
3.1170	Summary of Shift from Baseline in Systolic Blood Pressure
3.1180	Summary of Shift from Baseline in Diastolic Blood Pressure
3.1190	Summary of Shift from Baseline in Heart Rate
3.1200	Summary of Shift from Baseline in Temperature
3.1210	Summary of Frequency and Proportion of Subjects with Transfusions During the Trial
3.1220	Summary of ECG Findings at Screening
3.1222	Summary of Organ Examination Data Over Time by Investigator
3.1223	Summary of Organ Examination Data Over Time by the IRC
3.1230	Summary of Liver Chemistry Assessments for Subjects with Liver Signal/event
3.1240	Summary of Time on Treatment before Liver Event
3.1250	Summary of Subjects with Liver Chemistry Stopping Criteria for Dosing
3.1280	Summary of Blood Products and Blood Supportive Care Products
3.1282	Summary of Comparison of Grade $\geq 3$ Neutropenia Rates up to 60 Days After Last Treatment Using Modified Preferred Term
3.1283	Summary of Comparison of Grade $\geq 3$ Infection Rates up to 60 Days After Last Treatment
3.1300	Overview of Key Safety Summary by Type of Prior Treatment
3.1310	Summary of AEs with $\geq 5\%$ Incidence For all Grades and For

	Grade $\geq 3$ by Modified Preferred Term and Type of Prior Treatment
3.1320	Overview of Key Safety Summary by Number of Previous Induction Therapies
3.1340	Summary of AEs with $\geq 5\%$ Incidence For all Grades and For Grade $\geq 3$ by Modified Preferred Term and Number of Previous Induction Therapies
3.1350	Overview of Key Safety Summary by Type of Prior Chemoimmunotherapy
3.1360	Summary of AEs with $\geq 5\%$ Incidence For all Grades and For Grade $\geq 3$ by Modified Preferred Term and Type of Prior Chemoimmunotherapy
3.1370	Overview of Key Safety Summary by Response at Entry
3.1380	Summary of AEs with $\geq 5\%$ Incidence For all Grades and For Grade $\geq 3$ by Modified Preferred Term and Response at Entry
3.1390	Overview of Key Safety Summary by Age
3.1400	Summary of AEs with $\geq 5\%$ Incidence For all Grades and For Grade $\geq 3$ by Modified Preferred Term and Age
3.1410	Overview of Key Safety Summary by Gender
3.1420	Summary of AEs with $\geq 5\%$ Incidence For all Grades and For Grade $\geq 3$ by Modified Preferred Term and Gender
3.1430	Overview of Key Safety Summary by Race
3.1440	Summary of AEs with $\geq 5\%$ Incidence For all Grades and For Grade $\geq 3$ by Modified Preferred Term and Race
3.1450	Overview of Key Safety Summary by Geographic Region
3.1460	Summary of AEs with $\geq 5\%$ Incidence For all Grades and For Grade $\geq 3$ by Modified Preferred Term and Geographic Region
3.1470	Overview of Key Safety Summary by Modified RAI Stage
3.1480	Summary of AEs with $\geq 5\%$ Incidence For all Grades and For Grade $\geq 3$ by Modified Preferred Term and Modified RAI Stage
3.1490	Overview of Key Safety Summary by Binet Stage
3.1500	Summary of AEs with $\geq 5\%$ Incidence For all Grades and For Grade $\geq 3$ by Modified Preferred Term and Binet Stage
3.1510	Overview of Key Safety Summary by ECOG Status
3.1520	Summary of AEs with $\geq 5\%$ Incidence For all Grades and For Grade $\geq 3$ by Modified Preferred Term and ECOG Status
3.1530	Overview of Key Safety Summary by Cytogenetics Using 20% as the Cutoff
3.1540	Summary of AEs with $\geq 5\%$ Incidence For all Grades and For Grade $\geq 3$ by Modified Preferred Term and Cytogenetics Using 20% as the Cutoff
3.1550	Overview of Key Safety Summary by B2 Microglobulin ( $\leq 3500$ )

	vs >3500)
3.1560	Summary of AEs with $\geq 5\%$ Incidence For all Grades and For Grade $\geq 3$ by Modified Preferred Term and B2 Microglobulin ( $\leq 3500$ vs $>3500$ )
3.1570	Overview of Key Safety Summary by IgVH Mutational Status 1
3.1580	Summary of AEs with $\geq 5\%$ Incidence For all Grades and For Grade $\geq 3$ by Modified Preferred Term and IgVH Mutational Status 1
3.1590	Overview of Key Safety Summary by VH3-21 Usage Flag
3.1600	Summary of AEs with $\geq 5\%$ Incidence For all Grades and For Grade $\geq 3$ by Modified Preferred Term and VH3-21 Usage Flag
3.1700	Overview of Key Safety Summary by Screening Weight
3.1800	Time since last treatment with Ofatumumab for patients who have not started next anticancer therapy
PK	
5.0000	Summary of Plasma Ofatumumab Pharmacokinetic Concentration-Time Data (ug/mL)
Health Outcomes	
4.0000	Summary of Raw Score in EORTC QLQ-CLL 16 by Domain, Treatment and Visit
4.0010	Summary of Change from Baseline Score in EORTC QLQ-CLL 16 by Domain, Treatment and Visit
4.0050	Summary of Raw Score in EORTC QLQ-C30 by Domain, Treatment and Visit
4.0060	Summary of Change from Baseline Score in EORTC QLQ- C30 by Domain, Treatment and Visit
4.0100	Summary of Raw Score in Patient Reported B-symptoms by Domain, Treatment and Visit
4.0110	Summary of Change from Baseline Score in Patient Reported B-symptoms by Domain, Treatment and Visit
4.0120	Summary of Analysis of Change from Baseline Score in Patient Reported B-symptoms by Domain
4.0130	Summary of Change from Baseline Score in Patient Reported B-symptoms by Domain, Treatment and Visit for Subjects who had Investigator-Assessed Progression or Death
4.0150	Summary of Utility Score in EQ-5D by Treatment and Visit
4.0160	Summary of Change from Baseline Score in Utility Score in EQ-5D by Treatment and Visit
4.0200	Summary of Visual Analogue Scale (VAS) in EQ-5D by Treatment and Visit
4.0210	Summary of Change from Baseline in Visual Analogue Scale (VAS)

	in EQ-5D by Treatment and Visit
4.0250	Summary of Health Change Questionnaire by Treatment and Visit
Figures	
Figure No.	Title
Study Population	
11.0000	Graph of Percent Distribution of Age Group
Efficacy	
12.0010	Graph of Kaplan-Meier Investigator-Assessed Progression-Free Survival Curve
12.0020	Graph Of Kaplan-Meier Investigator-Assessed Progression-Free Survival Curve for the Per-protocol Population
12.0030	Graph of Kaplan-Meier Investigator-Assessed Progression-Free Survival Curve Including Events Based on CT-scan
12.0040	Graph of Kaplan-Meier IRC Assessed Progression-Free Survival Curve
12.0041	Graph of Kaplan-Meier Progression-Free Survival Based on Perceptives Sensitivity Analysis
12.0050	Graph of Kaplan-Meier Overall Survival Curve
12.0060	Graph of Kaplan-Meier Time to Next Therapy Curve
12.0070	Graph of Kaplan-Meier Investigator-Assessed Progression-Free Survival After Next-Line Therapy Curve
12.0080	Graph of Kaplan-Meier Investigator-Assessed Time to Progression After Next-line Therapy Curve
12.0090	Graph of Time to Response Assessment
12.0092	Graph of Kaplan-Meier Investigator-Assessed Time to Progression Curve
12.0100	Forest Plot of Hazard Ratios and 95% Confidence Intervals for Progression-Free Survival (Investigator-assessed, Investigator-Assessed including events determined by CT scan, IRC- Assessed with or without CT-scan)
12.0120	Forest Plot of Hazard Ratios and 95% Confidence Intervals for Investigator-Assessed Progression-Free Survival by Subgroups and Prognostic Markers
12.0121	Forest Plot of Hazard Ratios and 95% Confidence Intervals for Investigator Assessed Progression-Free Survival by Baseline Characteristics
12.0122	Forest Plot of Hazard Ratios and 95% Confidence Intervals for Investigator Assessed Progression-Free Survival by Prognostic Factors
12.0130	Graph of Hazard Ratio and 95% Confidence Intervals for Investigator-

	Assessed Progression-Free Survival Over Time
12.0140	Forest Plot of Hazard Ratios and 95% Confidence Intervals for Investigator Assessed Progression-Free Survival by Most Recent Type of Prior Chemoimmunotherapy and Best Response to Most Recent Type of Chemoimmunotherapy
Safety	
13.0011	Graph of Percent of Subjects Receiving Infusions During the Course of Treatment and the Percent of Subjects Having Infusion Reactions by Infusion for the Ofatumumab Arm
13.0012	Graph of Percent of Subjects Receiving Infusions During the Course of Treatment
13.0040	Graph of Median Hemoglobin Over Time
13.0050	Graph of Median Neutrophil Count Over Time
13.0060	Graph of Median Platelet Count Over Time
13.0070	Graph of Median IgG Over Time
13.0080	Graph of Median IgA Over Time
13.0090	Graph of Median IgM Over Time
13.0100	Graph of Median B-cell Over time
13.0110	Graph of Median Hemoglobin Over Time Excluding Subjects Who Received Blood or Blood Supportive Care Products During the Trial that Increase Hemoglobin
13.0120	Graph of Median Neutrophil Count Over Time Excluding Subjects Who Received Blood or Blood Supportive Care Products During the Trial that Increase Neutrophils
13.0130	Graph of Median Platelet Count Over Time Excluding Subjects Who Received Blood or Blood Supportive Care Products During the Trial that Increase Platelets
PK	
15.0010	Mean Plasma Ofatumumab Concentration-Time Plot (Linear and Semi-Log)
15.0020	Median Plasma Ofatumumab Concentration-Time Plot (Linear and Semi-Log)
15.0030	Individual Plasma Ofatumumab Concentration-Time Plot (Linear and Semi-Log)
Listings	
Listing No.	Title
Study Population	
21.0010	Listing of Randomized (planned) and Actual Treatments
21.0020	Listing of Subjects Excluded from the Per-protocol Population
21.0030	Listing of Reasons for Study Withdrawal
21.0040	Listing of Study Treatment Discontinuation Record

21.0050	Listing of Subjects with Inclusion/Exclusion Criteria Deviations
21.0060	Listing of Protocol Deviations
21.0070	Listing of Disease Characteristics at Initial Diagnosis
21.0071	Listing of Disease Characteristics at Screening
21.0080	Listing of Prior Treatment Anti-Cancer Therapy
21.0090	Listing of Post-Treatment Anti-Cancer Therapy
21.0100	Listing of Randomized and Actual Strata
21.0110	Listing of Concomitant Medications
21.0120	Listing of Most recent Prior Anti-cancer Therapies and Treatment Categories
21.0130	Listing of Most Recent Type of Prior Chemoimmunotherapies
Efficacy	
22.0010	Listing of Investigator-Assessed Progression-Free Survival
22.0020	Listing of Investigator-Assessed Progression-Free Survival with CT scan
22.0030	Listing of IRC Progression-Free Survival
22.0031	Listing of Progression-Free Survival Based on Perceptives Sensitivity Analysis
22.0040	Listing of Response Data
22.0050	Listing of Overall Survival
22.0060	Listing of Time to Next Therapy
22.0070	Listing of Investigator-Assessed Progression-Free Survival After Next Line Therapy
22.0080	Listing of Investigator-Assessed Time to Progression After Next Line Therapy
22.0090	Listing of ECOG Performance Status
22.0100	Listing of B-Symptoms
22.0110	Listing of CD5+CD19+ and CD5-CD19+
22.0120	Listing of Minimal Residual Disease Assessments
22.0130	Listing of Difference (Days) Between Investigator-Assessed Progression-Free Survival and IRC-Assessed Progression-Free Survival
Safety	
23.0010	Listing of Exposure to Ofatumumab
23.0020	Listing of Study Medication Compliance
23.0030	Listing of Dose Interruptions or Stops during Ofatumumab Infusion
23.0031	Listing of Reasons for Missed Doses
23.0070	Listing of All Adverse Events
23.0080	Listing of SAEs

23.0090	Listing of Subject Numbers for Specified Adverse Events
23.0100	Listing of All Non-Fatal Serious Adverse Events
23.0110	Listing of All Fatal Adverse Events
23.0120	Listing of Subject Numbers for Serious Adverse Events
23.0130	Listing of Adverse Events Leading to Permanent Discontinuation from Study Treatment
23.0140	Listing of Infections Reported as Adverse Events
23.0150	Listing of Opportunistic Infections
23.0160	Listing of Other Infections
23.0170	Listing of Terms for Infusion Reactions (within 24 hours of dosing) and Mucocutaneous Reactions Which Occurred During the Trial
23.0180	Listing of Infusion-related Adverse Events
23.0190	Listing of Mucocutaneous Reactions Adverse Events
23.0200	Listing of Autoimmune Hematologic Complication Adverse Events
23.0201	Listing of Tumor Lysis Syndrome Adverse Events
23.0202	Listing of Laboratory Data for Subjects with Tumor Lysis Syndrome
23.0210	Listing of Deaths
23.0220	Listing of Subject Numbers for Specific Causes of Death
23.0230	Listing of Chemistry Laboratory Data
23.0240	Listing of Hematologic Laboratory Data
23.0260	Listing of HAHA Data
23.0280	Listing of Vital Signs
23.0300	Listing of Blood Products and Blood Supportive Care Products
23.0330	Listing of Organ Examination Data Assessed by the Investigator
23.0332	Listing of Organ Examination Data Assessed by the IRC
23.0340	Listing of IgA, IgG, and IgM by Visit
23.0350	Listing of Liver Event Results and Time of Event Relative to Treatment
23.0360	Listing of Liver Chemistry Adverse Events for Subjects Reporting at Least one Liver Event
23.0370	Listing of Liver Chemistry Laboratory Data for Subjects Reporting at least one Liver Event
23.0380	Listing of Subjects with Lab Data with '<' or '>' Text
23.0390	Listing of Adverse Event Preferred Terms by Category of Infections
23.0400	Listing of First Prolonged Neutropenia
23.0410	Listing of Late-onset Neutropenia
23.0420	Listing of Relationship between Decreased Neutrophil Count from Baseline in Lab Dataset and Decreased Neutrophil Count in AE dataset

23.0430	Listing of Relationship between Decreased Neutrophil Count from Baseline in Lab Dataset and Decreased Neutrophil Count in AE dataset for data up to 60 days post last treatment
23.0440	Listing of Relationship between Decreased Hemoglobin from Baseline in Lab Dataset and Decreased Hemoglobin in AE dataset
23.0450	Listing of Relationship between Decreased Hemoglobin from Baseline in Lab Dataset and Decreased Hemoglobin in AE dataset for data up to 60 days post last treatment
23.0460	Listing of Relationship between Decreased Platelet Count from Baseline in Lab Dataset and Decreased Platelet Count in AE dataset
23.0470	Listing of Relationship between Decreased Platelet Count from Baseline in Lab Dataset and Decreased Platelet Count in AE dataset for data up to 60 days post last treatment
Health Outcomes	
24.0030	Listing of Health Change Questionnaire
PK	
25.0010	Listing of Plasma Ofatumumab Concentration-Time Data

Clinical Development

Ofatumumab/Arzerra®

OMB157C2301 / NCT01039376

**A phase III, open label, randomized, multicenter trial of ofatumumab maintenance treatment versus no further treatment in subjects with relapsed chronic lymphocytic leukemia (CLL) who have responded to induction therapy**

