2. OBJECTIVES

Primary objective:

[figure not shown]
- To evaluate PFS of subjects treated with ofatumumab maintenance treatment compared to no further treatment after remission induction in subjects with relapsed chronic CLL

Secondary objectives:

- To evaluate the improvement in response, improvement in response time to next CLL treatment and overall survival in subjects receiving ofatumumab maintenance compared to no further treatment
- To evaluate the PFS after next-line therapy and the time to progression after next-line therapy
- To evaluate the safety and tolerability in subjects with CLL receiving ofatumumab maintenance compared to no further treatment
- To evaluate the health-related quality of life in subjects with CLL receiving ofatumumab maintenance compared to no further treatment as assessed by changes in patient reported outcome (PRO) measures relative to baseline
- To evaluate prognostic marker correlation with clinical response in subjects with CLL receiving ofatumumab maintenance compared to no further treatment
- To evaluate ofatumumab pharmacokinetic parameters in subjects with CLL receiving maintenance ofatumumab every 2 months

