8.3.5.3. PRO Analyses

The EORTC QLQ-C30 and the EQ-5D will be scored as per the developers instructions, with scores created for each pre-specified domain. For the EORTC QLQ-CLL16, the developers have proposed a scoring, but it has not been validated yet. Therefore this scoring will be validated using the blinded data from the present trial.

In addition to the developer's hypothesized domains for both EORTC instruments it is also proposed that a 'B-symptoms' score will be created including the following items from the two instruments: need to rest (C30 item 10), felt weak (C30 item 12), tired (C30 item 18), weight loss (CLL item 31), temperature changes (CLL item 35), night sweats (CLL item 36), and skin problems such as itching (CLL item 37), lethargic (CLL item 39), slowed down (CLL item 40). This score is proposed to provide patient reported data that might be supportive of the constitutional symptoms assessment by the clinician.

Details of the scoring methods of all PRO measures will be provided in the RAP. Each PRO domain will be summarized for each treatment group and the total PRO sample at each time point will be presented in tabular format as mean, standard deviation, median, minimum, and maximum. Methods for imputation of missing data will be detailed in the RAP.

At each post-baseline timepoint, changes in PRO scores will be calculated by subtracting the baseline score from the score at the subsequent timepoint. Appropriate statistical tests will be proposed in the RAP to evaluate the significance of the change in scores over time, and to compare the scores between treatment arms.

Standard psychometric validation analyses will be performed for all PRO measures (EORTC QLQ C30, EORTC QLQ CLL16, 'B-Symptoms score', and EQ-5D). For the EORTC QLQ-CLL16 and B-Symptoms score, estimation of minimal clinically important differences will also be explored. Details of the methods for all of these psychometric validation analyses will be provided in the psychometric validation RAP.

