### Calculation of patient reported B-symptoms score

Since the psychometric validation has not been conducted at the time of RAP development, [REDACTED]

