**Summaries and Analyses:**

Changes from baseline scores over time in patient reported B-symptoms score will be analyzed with a repeated measures analysis of covariance (ANCOVA). Analyses will be carried out using PROC MIXED in SAS: baseline score, age group, performance status, and Binet stage, time, treatment, baseline by time, and treatment by time interaction will be fitted as fixed effects, and time will be treated as the repeated variable within subject. Restricted maximum likelihood (REML) will be used to estimate the parameters of the model. An unstructured variance-covariance matrix in the repeated measures model will be used. The model may be modified if required in order to obtain convergence.

Treatment comparisons, including estimated treatment difference, 95% confidence intervals and associated p-values will be provided.

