2.8110	Summary of Kaplan-Meier Estimates of Progression-Free Survival Based on Perceptives Sensitivity Analysis by Disease Score 2 – High/Very High Risk

2.8170	Summary of Best Response of First Next-Line Anti-cancer Therapy by Disease Score 2 – High/Very High Risk
2.8200	Summary of Kaplan-Meier Estimates of Investigator assessed Progression-Free Survival after next Line Therapy
2.8212	Summary of Duration of Response of First Prior Anti-Cancer Therapies (Duration is Based on End Date of First Regimen to Start Date of Second Regimen)  For subjects with Very High Risk/High Risk in Disease Score 2– High/Very High Risk
2.8213	Summary of Duration of Response of First Prior Anti-Cancer Therapies (Duration is based on end date of first regimen to start date of second regimen)
3.8000	Overview of Adverse Events by Disease Score 2 – High/Very High Risk
3.8010	Summary of Deaths by Disease Score 2 – High/Very High Risk
3.8020	Overview of Infections Reported as Adverse Events by Disease Score 2 – High/Very High Risk
3.8030	Overview of Adverse Events Associated with Decreased Neutrophil Counts by Disease Score 2 – High/Very High Risk
3.8032	Overview of Grade $\geq 3$ Adverse Events Associated with Decreased Neutrophil Counts by Disease Score 2 – High/Very High Risk
3.8050	Summary of treatment Duration (Days) by Disease Score 2 – High/Very High Risk
3.8060	Summary of Number of Cycles Treated by Disease Score 2 – High/Very High Risk
3.8130	Summary of Fatal SAEs for Subjects with High/Very High Risk in Disease Score 2 – High/Very High Risk
4.0020	Summary of Analysis of Change from Baseline Score in EORTC QLQ-CLL 16 by Domain
4.0030	Summary of Change from Baseline Score in EORTC QLQ-CLL 16 by Domain, Treatment and Visit for Subjects who had Investigator-Assessed Progression or Death
4.0040	Summary of Proportion of Subjects Experiencing a Drop or Rise in Score in EORTC QLQ-CLL 16 Using the Magnitude of MID (Estimated as 1/2 SD at Baseline) by Domain, Treatment and Visit
4.0070	Summary of Analysis of Change from Baseline Score in EORTC QLQ-C30 by Domain
4.0080	Summary of Change from Baseline Score in EORTC QLQ- C30 by

	Domain, Treatment and Visit for Subjects who had Investigator-Assessed Progression or Death
4.0090	Summary of Proportion of Subjects Experiencing a Drop or Rise in Score in EORTC QLQ- C30 Using the Magnitude of MID (Estimated as 1/2 SD at Baseline) by Domain, Treatment and Visit

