4.0140	Summary of Proportion of Subjects Experiencing a Drop or Rise in Score in Patient Reported B-symptoms Using the Magnitude of MID (Estimated as 1/2 SD at Baseline) by Domain, Treatment and Visit
4.0170	Summary of Analysis of Change from Baseline Score in Utility Score in EQ-5D
4.0180	Summary of Change from Baseline in Utility Score in EQ-5D by Treatment and Visit for Subjects who had Investigator-Assessed Progression or Death
4.0190	Summary of Proportion of Subjects Experiencing a Drop or Rise in Score in the Utility Score in EQ-5D Using the Magnitude of MID (Estimated as 1/2 SD at Baseline) by Treatment and Visit
4.0220	Summary of Analysis of Change from Baseline in Visual Analogue Scale (VAS) in EQ-5D
4.0230	Summary of Change from Baseline in Visual Analogue Scale (VAS) in EQ-5D by Treatment and Visit for Subjects who had Investigator-Assessed Progression or Death
4.0240	Summary of Proportion of Subjects Experiencing a Drop or Rise in Score in the Visual Analogue Scale (VAS) in EQ-5D Using the Magnitude of MID (Estimated as 1/2 SD at Baseline) by Treatment and Visit
12.7001	Graph of Kaplan-Meier Overall Survival Curve by IgVH Mutational Status 1
12.7002	Graph of Kaplan-Meier Overall Survival Curve by IgVH Mutational Status 1 (Excluding Not Available)
12.7003	Graph of Kaplan-Meier Overall Survival Curve by IgVH Mutational Status 2
12.7004	Graph of Kaplan-Meier Overall Survival Curve by IgVH Mutational Status 2 (Excluding Not Available)
12.7005	Graph of Kaplan-Meier Overall Survival Curve by IgVH Mutational Status 1 (includes missing IgVH)
12.8020	Graph of Kaplan-Meier Overall Survival Curve for subjects with very High Risk/High Risk Disease Score 2
12.8040	Graph of Kaplan-Meier Estimates of Investigator Assessed Progression-Free by Disease Score 2 - High/very High Risk

14.0000	Graph of Mean Change from Baseline of EORTC QLQ-CLL 16 with 95% CI by Domain
14.0010	Graph of Mean Change from Baseline of EORTC QLQ-CLL 30 with 95% CI by Domain
14.0020	Graph of Mean Change from Baseline of EQ-5D Utility Score with 95% CI
14.0030	Graph of Mean Change from Baseline of EQ-5D VAS Score with 95% CI
14.0060	Forest Plot of the Difference of Mean Change from Baseline Score (95% CI) in Patient Reported EORTC QLQ-CLL 16 by Domain
14.0070	Forest Plot of the Difference of Mean Change from Baseline Score (95% CI) in Patient Reported EORTC QLQ-C30 for the Symptom Scales

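### The 280-event plan drops the planned between-arm models for QLQ-C30, QLQ-CLL16 and EQ-5D, keeps only the B-symptoms model, and gives no reason

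*SAP*

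**What the plan says.** Protocol Section 2 makes quality of life a comparative secondary objective: "To evaluate the health-related quality of life in subjects with CLL receiving ofatumumab maintenance compared to no further treatment". Protocol 8.3.5.3 leaves the choice of tests to the analysis plan, but says that they are to assess change over time "and to compare the scores between treatment arms".

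SAP 13.1 meets this with a repeated-measures analysis of covariance on change from baseline in the B-symptoms score, fitted by REML with a treatment-by-time term. Its output is stated: "Treatment comparisons, including estimated treatment difference, 95% confidence intervals and associated p-values will be provided". SAP 13.2, 13.3 and 13.4 apply the same analysis to QLQ-CLL16, QLQ-C30 and EQ-5D. SAP 4.2 says that all available data are analysed at 280 events.

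The separate plan for the 280-event analysis opens with the interim PFS result (HR 0.50, 95% CI 0.38 to 0.66, p<0.0001). It then repeats every analysis of the interim study report except those in its Table 1. That table of exclusions includes:

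- "Summary of Analysis of Change from Baseline Score in EORTC QLQ-CLL 16 by Domain" (4.0020)
- "Summary of Analysis of Change from Baseline Score in EORTC QLQ-C30 by Domain" (4.0070)
- "Summary of Analysis of Change from Baseline Score in Utility Score in EQ-5D" (4.0170)
- the matching table for the EQ-5D VAS (4.0220)

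Appendix 1 of the same plan, the list of outputs to be produced, keeps "Summary of Analysis of Change from Baseline Score in Patient Reported B-symptoms by Domain" (4.0120). The last-visit plan has no health-outcomes block.

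**The concern.** Five model tables were due, all from the same specification, and four are withdrawn after the interim results were known in an open-label trial. The one that stays concerns a score of which SAP 13.1 says: "Since the psychometric validation has not been conducted at the time of RAP development". The last-visit plan still treats its validation as something that may or may not happen. Two of the instruments that lose their models are the ones the documents treat as validated: QLQ-C30 (Protocol 6.5.1) and EQ-5D (SAP 13.4).

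At stake is the evidence for a secondary objective that matters when an active infusion is compared with observation. For QLQ-C30, EQ-5D and QLQ-CLL16, the only adjusted estimate of the treatment difference would come from the interim cut. A reader of the 280-event report would see a modelled result for one score and could not tell why the others lack one.

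**Working it through.** **1. The output lists side by side.** Status in the 280-event plan (Table 1 for dropped, Appendix 1 for kept):

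| Output family | QLQ-CLL16 | QLQ-C30 | EQ-5D utility | EQ-5D VAS | B-symptoms |
|---|---|---|---|---|---|
| Scores by arm and visit | 4.0000 kept | 4.0050 kept | 4.0150 kept | 4.0200 kept | 4.0100 kept |
| Change by arm and visit | 4.0010 kept | 4.0060 kept | 4.0160 kept | 4.0210 kept | 4.0110 kept |
| Between-arm model | 4.0020 dropped | 4.0070 dropped | 4.0170 dropped | 4.0220 dropped | 4.0120 kept |
| Change in subjects with progression or death | 4.0030 dropped | 4.0080 dropped | 4.0180 dropped | 4.0230 dropped | 4.0130 kept |
| Shift by half a baseline SD | 4.0040 dropped | 4.0090 dropped | 4.0190 dropped | 4.0240 dropped | 4.0140 dropped |

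Models kept: 1 of 5 at 280 events, 0 of 5 at last visit. The forest plots of treatment differences for QLQ-CLL16 and QLQ-C30 (14.0060 to 14.0080) are dropped too.

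**2. Is this only a deferral?** The last-visit plan brings back some outputs dropped at 280 events (2.2020, 2.2052, 2.2053, 2.2070) but no patient-reported table. Its Table 2.2030 on B-symptoms sits under Efficacy, which matches the clinician-rated symptoms of SAP 11.2 rather than the questionnaire score.

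**3. Do the kept tables replace the model?** Protocol 6.5.6 expects questionnaires at progression and once more afterwards; later ones depend on the subject being available and willing. Interim median PFS was 29.4 against 15.2 months, so those still answering at late visits are probably selected differently in the two arms. The SAP model adjusts for baseline and uses all visits; raw visit means do neither. The model still relies on data being missing at random.

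**4. How much data does the interim cut leave out?** The 280 events are a PFS figure: 4(1.960 + 0.842)² / [ln(28/39.2)]² gives 278, in line with the plan. No patient-reported analysis was sized on it. The interim had 187/280 = 66.8% of those events, and the cut-offs of 19-Jun-2014 and 20-Feb-2017 are 32.1 months apart.

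The documents give no accrual curve, so I assume uniform accrual over T months before the interim cut-off:

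- T = 40: 479 evaluable subjects (Protocol 1.5) at the planned 12 per month (Protocol 8.2.1), 479/12 = 39.9.
- T = 48: a mid-2010 start, assumed from the date of Amendment 2 (21-May-2010).

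The share that could have reached t months is f = (T − t)/T. If all could reach t by the later cut-off, the standard error is multiplied by √f. Enrolment closed under Amendment 5 (26-Aug-2014), about 30 months before 20-Feb-2017, so all could reach 24 months.

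| Visit | T | f | √f | Reduction in SE |
|---|---|---|---|---|
| Month 25 (t = 24) | 40 | 16/40 = 0.40 | 0.63 | 37% |
| Month 25 (t = 24) | 48 | 24/48 = 0.50 | 0.71 | 29% |
| Month 13 (t = 12) | 40 | 28/40 = 0.70 | 0.84 | 16% |
| Month 13 (t = 12) | 48 | 36/48 = 0.75 | 0.87 | 13% |

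These figures ignore attrition and missed questionnaires. A contrast averaged over visits gains less than one at Month 25.

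**The case against.** The case for the sponsor is substantial, and most of it stands.

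- **Comparison by arm is not lost.** A reader might infer that the quality-of-life objective gets no mature comparison. The first two rows of the table above say otherwise, the Health Change Questionnaire (4.0250) is also kept, and the B-symptoms model is itself a later between-arm comparison. Only the modelled estimate for the other instruments is missing.
- **The B-symptoms score was not picked afterwards.** Protocol 6.5.4 and 8.3.5.3 define it, and SAP 13.1 uses it as the template for the other instruments. What came later was the choice to repeat its model alone.
- **Validation does not separate kept from dropped cleanly.** QLQ-CLL16 is unvalidated as well (Protocol 6.5.2, SAP 13.2). The contrast rests on QLQ-C30 and EQ-5D.
- **Selective reporting cannot be inferred.** The exclusion list is long and covers cytogenetic, B-cell, MRD, IgVH and disease-score outputs. It also removes some patient-reported B-symptoms outputs (4.0140, 14.0210). The repeat-except rule implies that the dropped models were run for the interim report. No patient-reported result appears in the documents, so a choice driven by such results cannot be shown.
- **No confirmatory claim changes.** The testing hierarchy covers time to next therapy and overall survival only, and the 280-event results are labelled descriptive.

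The descriptive label does not explain the asymmetry, because it applies equally to the B-symptoms model that was kept. An estimate with a confidence interval suits a descriptive analysis.

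**Conclusion.** The point holds as a reporting gap on a secondary objective. After 19-Jun-2014 there is no model-based between-arm estimate for QLQ-C30, EQ-5D or the also unvalidated QLQ-CLL16, although SAP 13 specifies one for each. The restriction is unexplained, favours one of five model tables, and was made after results were known. It is not evidence of motive.

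The size depends on accrual. Under uniform accrual over 40 to 48 months, the standard error would be about 29% to 37% smaller at Month 25 and about 13% to 16% smaller at Month 13, before attrition.

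One uncertainty remains. The last-visit plan cites a SAP of 02-Jun-2017 and an addendum of 11-Jan-2018. The documents do not show which of these the 280-event plan is, or whether the other changed the list.

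Table 2.2080, the prognostic-marker Cox model, is also dropped, but it serves a different objective, is partly covered by Figures 12.0120 and 12.0122, and forms no part of this point.

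**What to change.** Put Tables 4.0020, 4.0070, 4.0170 and 4.0220 back in the 280-event output list. Run them with the SAP 13 model on the data to 20-Feb-2017, and report treatment differences with 95% confidence intervals as descriptive estimates. Show Table 4.0120 beside them rather than alone. If the sponsor prefers not to, the plan should say why these four were left out and label the interim models as the only modelled results on those instruments.

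The cost is four tables. The 280-event plan implies that the programs exist from the interim report, so this is a rerun on a later data cut, with no new data collection.
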